#### **5.4.3. Medical history and concomitant diseases**

Summary tables (number and % of patients) grouped by SOC and PT will be presented for Medical history firstly then for concomitant diseases by series and overall for Medical history firstly then for concomitant diseases using FAS1, FAS2 and by contrast agent group using Safety set. Tables will be sorted by descending frequency of SOC and, within each SOC, by descending frequency of PT. Same analyses will be repeated by body regions using FAS1 and FAS2 only.

Listing of medical history and concomitant diseases will be presented in CSR Appendix 16.2.4.

#### **5.4.4. Clinical laboratory evaluation at baseline**

eGFR data will be presented at V2 and V4 using the safety set by contrast agent group. eGFR data will be analyzed quantitatively and qualitatively. Qualitative analyses will present number of patients with value <30 mL/min/1.73m^2, ≥30 and <60 mL/min/1.73m^2, ≥60 and <90 mL/min/1.73m^2, ≥90 mL/min/1.73m^2. Quantitative analyses will be done by tabulating raw data.

Listing of eGFR data will be presented in CSR Appendix 16.2.8.

#### **5.4.5. Vital signs, physical findings and other observations related to safety at baseline**

Physical examination not performed and reason will be listed in CSR Appendix 16.2.4. Vital signs will be only presented in the safety section.

#### **5.4.6. Prior medications**

Summary tables (number and % of patients) grouped by the first and the fourth level of Anatomical Therapeutic Chemical (ATC) code will be presented by series and overall for prior medication using FAS1 and FAS2. Tables will be sorted by descending frequency of ATC1 (anatomical class) and, within each ATC1, by descending frequency of ATC4 (chemical class) according to the overall column. The ATC4 code will be added to the name in the table.

Listing of prior therapies will be presented in CSR Appendix 16.2.4.

#### **5.4.7. Other baseline characteristics**

Frequency and percentages will be tabulated by contrast agent group and overall for patient intolerance history related to contrast agent using Safety set.

Listing of patient intolerance history related to contrast agent will be presented in CSR Appendix 16.2.4

CONFIDENTIAL	STATISTICAL ANALYSIS PLAN PHASE III TRIAL GDX-44-011 VERSION NO. 2.0      DATED 25 JANUARY 2021	████████ Page 27 / 57
--------------	---	--------------------------

## 5.5. MRI examination

MRI examination will be presented using the FAS1 and FAS2. Analysis using FAS 1 will show only MRI examination when gadopiclenol is administered. Analysis using FAS 2 will show MRI examination by contrast agent group.

MRI examination performed, magnetic field strength (1.5 or 3.0 tesla) and body regions will be tabulated by contrast agent group.

Listing of MRI examination and body regions will be presented in CSR Appendix 16.2.5.

## 5.6. Efficacy evaluation

### 5.6.1. Primary analysis of the primary criteria

#### Superiority of Paired versus Pre contrast images of gadopiclenol regarding lesion visualization co-primary criteria (primary criteria 1)

Each co-primary criterion will be analyzed using a general linear model for each reader independently, modelling the patient's score as a function of the MRI modality ("Pre" MRI and "Paired" MRI) with adjustment on repeated measures on the patient due to the pairing of MRI modalities in patients.

Hence for each off-site reader, the models will be the following:

- Border delineation = MRI modalities + error
- Internal morphology = MRI modalities + error
- Degree of contrast enhancement = MRI modalities + error

The parameters of the general linear model will be estimated using the SAS® procedure Mixed. The procedure used for the superiority analysis will be the following for each co-primary criterion and each off-site reader:

```
proc mixed data = XXX method = REML;
  class subject MRI;
  model eval = MRI;
  repeated MRI / subject=subject / type = cs;
/* To get the one-sided p-value of the paired t-test*/
  lsmeans MRI / pdiff = controlu('PRE') tdiff cl alpha = 0.025;
/* To get the estimate and the corresponding confidence interval of the paired difference */
  lsmeans MRI;
  estimate "PAIRED - PRE" MRI 1 -1 /cl;
run; .
```

For gadopiclenol, the difference "Paired" -"Pre" for each of 3 co-primary criteria will be analyzed using two-sided paired t-tests on the FAS1 on matching lesions. Results will be presented per off-site reader.

In order that superiority of the "Paired" MRI over the "Pre" will be statistically demonstrated, 2 out of 3 readers will have to meet the alternative hypothesis for the three co-primary criteria in the gadopiclenol group: a statistically significant (one-sided p-value is equal or less than 0.025) positive difference in mean scores in border delineation, internal morphology and degree of contrast enhancement of lesions.

#### Non-inferiority of gadopiclenol versus gadobutrol regarding lesion visualization co-primary criteria (primary criteria 2)

CONFIDENTIAL	STATISTICAL ANALYSIS PLAN PHASE III TRIAL GDX-44-011 VERSION NO. 2.0      DATED 25 JANUARY 2021	████████ Page 28 / 57
--------------	---	--------------------------

Each co-primary criterion will be analyzed using a general linear model for each reader independently, modelling the patient's score as a function of the contrast agent group (GBCA: gadopiclenol and gadobutrol) with repeated measures on the patient due to the pairing of contrast agents in patients.

Hence for each off-site reader, the models will be the following:

- Border delineation = contrast agent group + period + error
- Internal morphology = contrast agent group + period + error
- Degree of contrast enhancement = contrast agent group + period + error

The parameters of the general linear model will be estimated using the SAS® procedure Mixed. The procedure used for the non-inferiority analysis will be the following for each co-primary criterion and each off-site reader:

```
proc mixed data = XXX method = REML;
  class subject GBCA period;
  model eval = GBCA period;
  repeated GBCA / subject=subject / type = cs;
/* To get the estimate and the corresponding confidence interval of the paired difference */
  lsmeans GBCA;
  estimate "gadopiclenol - gadobutrol" GBCA 1 -1 /cl;
run;
```

The Student's t-based 95% confidence intervals of the difference between gadopiclenol and gadobutrol will be constructed for each of 3 co-primary criteria using the PPS2 on matching lesions. Results will be presented per off-site reader.

If the lower bound of this confidence interval is above the non-inferiority margin for at least 2 out of 3 readers and for the 3 co-primary criteria, then non-inferiority between gadopiclenol and gadobutrol will be concluded.

As soon as the non-inferiority is demonstrated, the superiority of the gadopiclenol over gadobutrol will be tested using the same method. No adjustment for multiplicity is needed as it is a simple closed testing procedure.

If the lower bound of the Student's t-based 95% confidence intervals of the difference between gadopiclenol and gadobutrol is above 0 for at least 2 out of 3 readers and for the 3 co-primary criteria, then superiority of gadopiclenol over gadobutrol will be concluded.

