### Lesion visualization at lesion level (off site read)

Each lesion visualization criterion will be analyzed by reader using a general linear model, modelling the lesion score as a function of the reader, center, period and on the one hand contrast agent group (GBCA: gadopiclenol and gadobutrol) with repeated measures on the lesion due to the pairing of contrast agents in lesions and on the other hand, modality of the MRI (pre and paired images) with repeated measures on the lesion due to the pairing of MRI modalities or contrast agent group in lesions. Matching and no matching lesions will be kept in the analysis.

Hence the models will be the following for gadobutrol vs. gadopiclenol:

- Border delineation = contrast agent group + period + reader + center + error
- Internal morphology = contrast agent group + period + reader + center + error
- Degree of contrast enhancement = contrast agent group + period + reader + center + error

and the following for pre vs. paired within gadopiclenol MRI period:

- Border delineation = MRI modality + period + reader + center + error
- Internal morphology = MRI modality + period + reader + center + error
- Degree of contrast enhancement = MRI modality + period + reader + center + error

The parameters of the general linear model will be estimated using the SAS® procedure Mixed. The procedure used for the analysis will be the following for each criterion:

proc mixed data = XXX method = REML;

class lesion # GBCA (or MRI modality) period reader center;

model eval = GBCA(or MRI modality) period reader center;

repeated GBCA(or MRI modality) / subject=lesion # / type = cs;

/\* To get the estimate and the corresponding confidence interval of the paired difference \*/

```

proc mixed data = XXX method = REML;
  class lesion_# GBCA (or MRI modality) period reader center organ;
  model eval = GBCA (or MRI modality) period reader center organ;
  repeated GBCA (or MRI modality) / subject=lesion_# / type = cs;
/* To get the estimate and the corresponding confidence interval of the paired difference */
  lsmeans GBCA (or MRI modality);
  lsmeans GBCA (or MRI modality) * organ
  estimate "gadopiclenol - gadobutrol" GBCA (or "Paired - Pre" MRI modality) 1 -1 /cl;
  estimate "gadopiclenol - gadobutrol" GBCA (or "Paired - Pre" MRI modality) *organ ... /cl;
run;

```

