### Number of lesions

The number of lesions by patient will be assessed by off-site readers and on-site radiologists and will be tabulated (as quantitative parameter and in class: No lesion / 1 lesion / 2 lesions / 3 lesions / More than 3

CONFIDENTIAL	STATISTICAL ANALYSIS PLAN PHASE III TRIAL GDX-44-011 VERSION NO. 2.0      DATED 25 JANUARY 2021	████████ Page 36 / 57
--------------	---	--------------------------

lesions) by contrast agent groups and MRI modalities (pre and paired); off-site and on-site reader's outcomes will be separately analyzed. Matching and no matching lesions will be kept in the analysis.

The number of lesions will be fitted by a multivariate model using the negative binomial distribution. The model will include the factors period contrast agent group and MRI modalities (pre and paired). Each off-site reader will be analyzed by a specific model and on-site reading will be analyzed in the same way. The parameters of the model will be estimated using the SAS® procedure Glimmix. The difference between contrast agent groups using extended FAS2 and between MRI modalities using extended FAS1 in mean of lesions detected and associated 95% CI will be computed.

Procedure used will be the following for each off-site reader and on-site reading:

Paired vs Pre analysis in Gadopiclenol group using extended FAS1:

```
proc glimmix data = XXX;
  class subject MRI period;
  model nblesions = MRI period / dist = negbin link = id;
  random _residual_ / subject = subject;
  lsmeans MRI/ pdiff = controlu('PRE') tdiff cl alpha = 0.025;
  lsmeans MRI;
  estimate "Paired - Pre" MRI 1 -1 /cl;
run;
```

Paired Gadopiclenol vs Paired Gadobutrol using extended FAS2:

```
proc glimmix data = XXX;
  class subject GBCA period;
  model nblesions = GBCA / dist = negbin link = id;
  random _residual_ / subject = subject;
  lsmeans GBCA / pdiff = controlu('gadobutrol') tdiff cl alpha = 0.025;
  lsmeans GBCA;
  estimate "gadopiclenol - gadobutrol" GBCA 1 -1 /cl;
run;
```

Subgroup analyses by body region and organ as described in the section additional analysis of the primary criteria will be conducted for number of lesions.

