**Impact of contrast-enhanced MRI on patient treatment plan**

The impact on patient treatment plan will be tabulated by contrast agent groups. The therapeutic management proposed based on combined unenhanced and contrast-enhanced MRI vs the one based on unenhanced MRI will be tabulated for all patients having the treatment plan be changed.

The impact on patient treatment plan will be tabulated by contrast agent groups and tumor classification before GBCA administration.

The tumor classification is based on diagnosis done at unenhanced MRI according to the following:

Diagnosis	Tumor classification
Negative	Non Malignant
Benign	Non Malignant
Probably Benign finding	Non Malignant
Low Suspicion of Malignancy	Malignant
Intermediate Suspicion of Malignancy	Malignant
Moderately High Suspicion of Malignancy	Malignant
Not assessable	Not assessable

The impact on patient treatment plan will be fitted by a multiple logistic regression model for correlated data. The model will include the factors contrast agent group and tumor classification before administration (malignant / non malignant / not assessable). The parameters of the model will be estimated using the SAS® procedure glimmix. The difference between contrast agent groups in proportions and associated 95% CI will be computed globally and for each tumor classification.

```
proc glimmix data = XXX;
  class subject GBCA tumor_cl;
  model eval = GBCA tumor_cl GBCA*tumor_cl / dist = bin link =I d ddfm = kr;
  random _residual_ / subject = patient type = cs;
  estimate "gadopiclenol - gadobutrol" GBCA -1 1 /cl;
  estimate "gadopiclenol - gadobutrol for malignant tumor" GBCA -1 1 GBCA*tumor_cl -1 0 0 1 0 0 /cl;
  estimate "gadopiclenol - gadobutrol for non malignant tumor" GBCA -1 1 GBCA*tumor_cl 0 -1 0 0 1 0 /cl;
  estimate "gadopiclenol - gadobutrol for not assessable tumor" GBCA -1 1 GBCA*tumor_cl 0 0 -1 0 0 1 /cl;
run;
```

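### The SAS code for primary objective 2 does not secure the sign of gadopiclenol minus gadobutrol: the same label has opposite coefficients elsewhere in the SAP, and no level order is stated

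*SAP*

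**What the plan says.** The intended direction is not in doubt. Protocol 11.1 and SAP 3.3 (number of patients for primary objective 2) both define the analysed quantity as the gadopiclenol-gadobutrol difference. SAP 5.6.1 requires its lower 95% bound to lie above the margin, and then above 0 for a claim that gadopiclenol is superior.

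The printed code is less settled:

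- SAP 5.6.1, primary criteria 2: "estimate 'gadopiclenol - gadobutrol' GBCA 1 -1 /cl". The only other statement in that program that reports on the agents is a plain LSMEANS for GBCA, which gives the two means but requests no difference.
- SAP 5.6.2, impact on the treatment plan: "estimate 'gadopiclenol - gadobutrol' GBCA -1 1 /cl".
- SAP 5.6.2, lesion-level analysis, where one line serves two labels: "estimate 'gadopiclenol - gadobutrol' GBCA (or 'Paired - Pre' MRI modality) 1 -1 /cl". The programs for lesion size, number of lesions, percentage enhancement and lesion-to-background ratio also use 1 -1.
- SAP 5.6.1, primary criteria 1: "estimate 'PAIRED - PRE' MRI 1 -1 /cl". Here the p-value comes from a separate statement that names its reference: "lsmeans MRI / pdiff = controlu('PRE') tdiff cl alpha = 0.025".
- SAP 5.6.2, number of lesions, which names the comparator in the same way: "lsmeans GBCA / pdiff = controlu('gadobutrol') tdiff cl alpha = 0.025".

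No CLASS statement carries an ordering option, format or numeric coding. In the primary section the GBCA levels appear only in a descriptive phrase: "as a function of the contrast agent group (GBCA: gadopiclenol and gadobutrol".

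**The concern.** On a two-level factor, 1 -1 and -1 1 are exact negatives, so what each line estimates depends on which level the software puts first. With one common level order and the 'yes' event modelled in the treatment-plan program, one of the two lines must contradict its label.

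The primary criteria 2 program is the exposed one. Its ESTIMATE line is the only printed source of the interval that decides primary objective 2 for EMA and the follow-on superiority claim. A reversed sign turns an interval (L, U) into (-U, -L). The lower-bound rule would then be checking that gadopiclenol is not too much better than gadobutrol, instead of not too much worse.

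**Working it through.** **The plan's own figure.** SAP 3.3 gives 200 evaluable patients from margin 0.35, SD of the difference 1.75, true difference 0, 80% power and a two-sided 95% interval. For a paired comparison, n = (SD × (z0.975 + z0.80) / margin)² = (1.75 × 2.802 / 0.35)² ≈ 196.2, so 197. With the t distribution 199 are needed, and power at 200 is 80.4%. Allowing for 33% non-evaluable patients, 200 / 0.67 gives 299, against 300 planned. The sample size reproduces and is not at issue.

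**What each line returns under the two possible GBCA orders.**

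| Level order | Primary criteria 2 line (1 -1) | Treatment-plan line (-1 1), 'yes' modelled |
|---|---|---|
| gadopiclenol, gadobutrol | gadopiclenol minus gadobutrol: matches label | gadobutrol minus gadopiclenol: contradicts label |
| gadobutrol, gadopiclenol | gadobutrol minus gadopiclenol: contradicts label | gadopiclenol minus gadobutrol: matches label |

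Sorting by name puts gadobutrol before gadopiclenol, and PAIRED before PRE. The primary criteria 1 line and the treatment-plan line then match their labels, and the primary criteria 2 line does not. Two features are compatible with name order. Several programs in SAP 5.6.2 use gadobutrol as a text level. The treatment-plan interaction coefficients also run malignant, non malignant, not assessable. The second sign is weak, because the prose lists the three classes in the same order.

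**Size, if gadobutrol is the first level and nobody notices.** Inputs: n = 200, 198 df (period is in the model), critical t = 1.972, margin read as -0.35 on gadopiclenol minus gadobutrol (the documents print 0.35 without a sign), one reader, one criterion.

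Half-width h = 1.972 × SD / √200. The correct sign passes when the observed difference is above -0.35 + h. The reversed sign passes when it is below 0.35 - h.

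| SD (SAP 3.3) | h | Correct: passes above | Reversed: passes below | Decisions differ when the true difference is 0 |
|---|---|---|---|---|
| 1.75 | 0.244 | -0.106 | +0.106 | 39% |
| 1.15 | 0.160 | -0.190 | +0.190 | 2.0% |
| 0.7 | 0.098 | -0.252 | +0.252 | 0% |

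The last column comes from 400,000 simulated data sets.

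Example at SD 1.75: an observed -0.20 has the interval -0.20 ± 0.244, or -0.444 to 0.044. Its lower bound is below -0.35, so it fails. Reversed, the interval is -0.044 to 0.444 and it passes.

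Probability of concluding non-inferiority at SD 1.75, from the noncentral t with standard error 1.75/√200 = 0.1237:

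| True difference | Correct sign | Reversed sign |
|---|---|---|
| -0.35 | 2.5% | 99.99% |
| -0.175 | 29.0% | 98.8% |
| 0 | 80.4% | 80.4% |

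**The case against.** The strongest reply is that nothing shows the primary line to be wrong. Three parts of it stand.

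- A reader might infer that no single convention makes both primary ESTIMATE lines match their labels. That is not so. Coding the test condition first and the comparator second fits both, and the SAP's headings use that order (Paired versus Pre; gadopiclenol versus gadobutrol). The model sentence for primary criteria 1 runs the other way, "as a function of the MRI modality ('Pre' MRI and 'Paired' MRI", so order of mention is no guide, but a test-first coding remains possible. It is simply not written down.
- A reader might infer that the two opposite lines cannot both be right under one level order. For a yes/no outcome they can. With gadopiclenol first and 'no' modelled on what appears to be an identity link, -1 1 gives P(no | gadobutrol) - P(no | gadopiclenol). This equals P(yes | gadopiclenol) - P(yes | gadobutrol), as labelled. The SAP states no event, so the treatment-plan line alone does not convict the primary line.
- The code is schematic (placeholder data set names, doubled slashes, alternatives in parentheses) and must be edited before it runs. The LSMEANS for both agents are printed beside the estimate. Descriptive tables by agent are planned (SAP 5.6.2), the body-region sensitivity analysis uses gadobutrol as named control, and SAP 3.1 requires quality control by the CRO. An unnoticed reversal is unlikely.

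The reply does not remove the point. SAP 5.6.1 presents this as the procedure that will be used. The SAP asks for no sign check, and it uses the order-proof construction in secondary analyses while leaving it out of the one program where the interval decides a primary objective.

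**Conclusion.** The point holds as an inconsistency to remove before the analysis is run. The prose fixes the direction; the printed programs do not secure it and disagree under the same label. The primary criteria 2 line is reversed only if gadobutrol is the first level. That rests on an assumed ordering by name, which the documents neither state nor exclude. If gadopiclenol is first, the primary analysis is unaffected, and the treatment-plan line needs correction or a stated event.

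The contrast of 2.5% with 99.99% is a conditional worst case and should not be read as the trial's error rate. It needs the reversed coding, the printed line kept as it is, every cross-check missed and a true difference at the margin. It also covers one reader and one criterion, whereas the rule requires at least two of three readers on all three criteria. At the planned true difference of 0 the pass probability does not change. At the SDs that SAP 3.3 derives from phase IIb (0.7 to 1.15), the two signs then give different decisions in 0% to 2.0% of data sets.

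One limit: part of SAP 3.2 to 3.3 is missing from the copy reviewed, so any statement there of the objective 2 hypotheses could not be checked. The point is worth fixing because the deciding interval depends on it and the correction is trivial.

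**What to change.** In the primary criteria 2 program, take the difference and its two-sided 95% interval (alpha = 0.05) from LSMEANS with gadobutrol as the named control; this does not depend on level order. Alternatively, state the GBCA and MRI level orders in SAP 5.6.1.

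In either case, state the modelled event in the treatment-plan program. Make every ESTIMATE line labelled gadopiclenol minus gadobutrol agree with the stated order, including the interaction lines in the body-region, organ, demographic, lesion-level, lesion-size and treatment-plan programs.

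The cost is one or two sentences and single-line code edits. No patients, new data, sample size or decision rule are affected.

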## 5.6.2. Secondary analysis

### Additional analyses of the primary analyses

#### Supportive analyses of the superiority analysis

The superiority analysis will be repeated using the PPS1.

#### Supportive analyses of the non-inferiority analysis

The non-inferiority analysis will be repeated using the FAS2.

#### Descriptive statistics

The 3 co-primary criteria will be summarized by contrast agent groups and MRI modalities (pre & paired) using the FAS1, FAS2, PPS1 and PPS2. Analyses using FAS1 and PPS1 will show only co-primary criteria when gadopiclenol is administered.

CONFIDENTIAL	STATISTICAL ANALYSIS PLAN PHASE III TRIAL GDX-44-011 VERSION NO. 2.0	████████ Page 29 / 57
--------------	--	--------------------------

Assay sensitivity:

For MRI with gadobutrol, the difference “Paired” -”Pre” for each of 3 co-primary criteria will be analyzed using the same analysis as described for superiority on the FAS2. Results will be presented per off-site reader.

Examinations of subgroups

**Body region**

Descriptive statistics:

The 3 co-primary criteria will be summarized by contrast agent groups, MRI modalities (pre and paired) and body regions using FAS1 and FAS2. Analysis using FAS 1 will show only co-primary criteria when gadopiclenol is administered.

Model:

In addition to the primary analyses, sensitivity analyses of the superiority analysis (on the FAS1) and of the non-inferiority analysis (on the FAS2) will be conducted using the same linear model with body region as additional factors.

The model syntax will be as follows for the sensitivity analysis of the superiority:

```
proc mixed data = XXX method = REML;
  class subject MRI body;
  model eval = MRI body MRI*body;
  repeated MRI / subject=subject / type = cs;
  lsmeans MRI body MRI*body / pdiff = controlu('PRE') tdiff cl alpha = 0.025;
  estimate "PAIRED - PRE" MRI*body 1 -1 ..../cl;
run; .
```

The model syntax will be as follows for the sensitivity analysis of the non inferiority:

```
proc mixed data = XXX method = REML;
  class subject GBCA body period;
  model eval = GBCA body period GBCA *body;
  repeated GBCA / subject=subject / type = cs;
  lsmeans GBCA body GBCA*body / pdiff = controlu('gadobutrol') tdiff cl alpha = 0.025;
  estimate "gadopiclenol - "gadobutrol" GBCA*body 1 -1 ..../cl;
run; .
```

The robustness of MRI modality or GBCA effect across different body regions will be discussed with following information:

- Descriptive summary statistics for each body region
- Body region effect and body region \*MRI modality/GBCA interactions tests. These tests are used as exploratory indexes meaning that conclusions of these tests are just used as a support for discussion. Absence of statistical significance should not be taken to imply consistency. Absence of statistical significance in an interaction test, or only directional consistency, would not be sufficiently sensitive filters to detect differences of potential interest.
- Effect estimations for each body region with the associated 95% two-sided CI. Overlapping of all body regions CI estimates with the confidence interval for the overall effect will be checked.
- Graphical visualization of the Body regions with a Forest plot for each body region of the LS Means difference and also the LS Means Ratio.

